8.8.2 Optional Cell-free DNA Analysis Sample Collection

Two blood samples for cell-free DNA analysis (see SoA; Table 1) will be collected from participants who have consented to participate in the genomic analysis component of the study. Participation is optional. Participants who do not wish to participate in the genetic research may still participate in the study.

8.9 Medical Resource Utilisation and Health Economics

Health economics/Medical resource utilisation and health economics parameters are not evaluated in this study.

^{*} will not be delivered prior to database lock and will not be part of the CSR.

9 STATISTICAL CONSIDERATIONS

The SAP will be finalised prior to database lock and it will include a more technical and detailed description of the planned statistical analyses. This section is a summary of the planned statistical analyses of the most important endpoints including primary and key secondary endpoints.

9.1 Statistical Hypotheses

Null hypothesis that there is no difference in the time to first COPDCompEx event in mitiperstat (AZD4831) 5 mg QD vs placebo with an alternative hypothesis that there is a difference in the time to first COPDCompEx event. As a single logrank test, adjustment for multiple testing will not be required.

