9.2 Sample Size Determination

The study is powered using COPDCompEx, a composite endpoint used to predict treatment effect on moderate and severe exacerbations of COPD (see Section 8.2.1).

The time to first COPDCompEx event will be compared between mitiperstat (AZD4831) 5 mg QD vs placebo arms using a logrank test. A total of 194 first COPDCompEx events (estimated to require 203 participants per arm) will provide 80% power at the two-sided 10% level of statistical significance to detect a hazard ratio of 0.70 in the mitiperstat (AZD4831) 5 mg QD arm based on a 24-week first COPDCompEx event risk of 55% assumed in the placebo arm (constant over the course of the study).

A screen failure rate of 40% is assumed, therefore approximately 677 participants will be screened to achieve randomisation of 406 participants.

For all other secondary or exploratory endpoints, no formal sample size calculation was performed. Further information is available in the SAP.

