3.3.5 Multiplicity/Multiple Comparisons

No multiplicity/multiple comparison are planned for this study.

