3.4.3 Mixed Model Repeated Measures (MMRM)

The MMRM model will be used to fit change from baseline for continuous endpoints that have data at several post-baseline visits. The model will include all available data from all visits, irrespective of whether the patient discontinued study intervention. Since a repeated measures model is being applied, no imputation will be made for missing data. Region will be added as a random effect. The model will include fixed effects for baseline, visit, study intervention and the baseline by visit and study intervention by visit interactions. An unstructured covariance matrix will be used to describe the correlations on a patient between visits, and the Kenward-Roger correction will be used for degree of freedom approximation in the generation of the model. In the event that the model with unstructured covariance matrix fails to converge, an alternative such as autoregressive or compound symmetry will be used instead. Estimates of the least square (LS) mean change from baseline for each study intervention, and the difference between them (AZD4831-placebo), together with two-sided 90% CI, will be obtained from the model for each visit. The study intervention effect will be tested at the 10% two-sided level of significance.

The reportable results from the model are:

- The LSmeans change from baseline at each visit and their standard errors for each study intervention group.
- The difference in change from baseline at each visit between AZD4831 and placebo (LSmeans difference) together with its two-sided 90% confidence interval (CI).
- The two-sided p-value for the difference in change from baseline at each visit between AZD4831 and placebo.

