4.2.2.4 Primary Analysis of Secondary Endpoint

Kaplan-Meier curves, region-stratified logrank test and region stratified Cox proportional hazard model results, will be provided for time to first moderate or severe exacerbation as specified in Section 3.4.1.

A two-sided region-stratified logrank test p-value ≤ 0.10 is required to provide evidence of efficacy. Kaplan-Meier curve estimates will be provided with a 90% CI.

Survival probabilities will be presented as survival curves estimated using the Kaplan-Meier method.

Diagnostic plot (log-log) will be presented to assess proportional hazard assumption.

The hazard ratio estimate from the Cox PH model will be provided with a 90% CI.

Exacerbations data will be listed.

The analysis will be focused on the FAS population.

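### The reason given for no multiplicity adjustment covers only the primary logrank test, while the SAP gives time to first moderate or severe exacerbation a second, ungated efficacy rule at the full two-sided 10%

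*Protocol*

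**What the plan says.** Protocol 9.1 states one null hypothesis, on time to first COPDCompEx event, and concludes: "As a single logrank test, adjustment for multiple testing will not be required". Protocol 9.2 attaches the error rate and power to that test: 194 first events "will provide 80% power at the two-sided 10% level of statistical significance to detect a hazard ratio of 0.70". Protocol 9.4.2.1 and SAP 4.2.1.4 make a two-sided logrank p ≤ 0.10 the condition for evidence of efficacy on this endpoint; the SAP version is stratified by region.

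Protocol 9.4.2.2 then carries a similar approach over to time to first exacerbation. SAP 4.2.2.4 turns this into an explicit rule for that endpoint: "A two-sided region-stratified logrank test p-value ≤ 0.10 is required to provide evidence of efficacy". No sentence makes it depend on the primary result.

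On multiplicity, SAP 3.3.5 says only: "No multiplicity/multiple comparison are planned for this study". Neither document sets a testing hierarchy, describes secondary p-values as nominal, or states a familywise error rate.

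**The concern.** The waiver rests on there being one test. Once a second endpoint has its own rule for declaring efficacy, at the same full 10% and with no gate, that reason no longer describes the plan.

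The practical question is a split result: the primary misses p ≤ 0.10 and the exacerbation test meets it. As written, SAP 4.2.2.4 allows evidence of efficacy to be stated, and nothing in either document says how this should be read beside a failed primary. The case is a natural one to foresee. Protocol 4.2 describes COPDCompEx as a novel surrogate composite, and exacerbations are the outcome it is meant to predict, so a favourable exacerbation result would draw attention whatever the primary showed. Protocol 9.2 makes no formal sample size calculation for this endpoint.

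**Working it through.** **1. The plan's own figure.** Inputs from Protocol 9.2 and 4.1: hazard ratio 0.70, two-sided 10%, 80% power, 1:1 allocation.

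Schoenfeld events = 4 × (1.645 + 0.842)² / (ln 0.70)² = 194.4. The plan states 194, which gives 79.9% power. Two-sided 5% would need 247 events and one-sided 10% would need 142, so the stated level is indeed two-sided 10%.

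For participants, a 55% placebo risk gives a treated risk of 1 − 0.45^0.7 = 42.8% and a mean risk of 48.9%. Then 194 / 0.489 = 397, within 3% of the planned 406. The primary design reproduces. Its type I error is 10%, and a second test on another endpoint does not alter it.

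**2. Two rules, both nulls true.** If the tests are independent, the chance that at least one gives p ≤ 0.10 is 1 − 0.90² = 19.0%. The Bonferroni bound is 20%. In the beneficial direction each test has 5%, so the chance is 1 − 0.95² = 9.75%.

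**3. Correlated tests.** Moderate or severe exacerbations are a component of COPDCompEx (SAP 4.2.1.1), so the two statistics should be positively correlated. The documents give no value, so the correlations below are assumptions. With bivariate normal statistics and critical value 1.645, the two-sided figure is 1 − P(|Z1| < 1.645 and |Z2| < 1.645), and the beneficial-direction figure is 1 − P(Z1 < 1.645 and Z2 < 1.645), taking positive Z as benefit.

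| Assumed correlation | At least one rule met, two-sided | Beneficial direction only |
|---|---|---|
| 0 | 19.0% | 9.75% |
| 0.3 | 18.5% | 9.3% |
| 0.5 | 17.6% | 8.8% |
| 0.7 | 16.1% | 8.0% |
| 0.9 | 13.6% | 6.8% |
| 1 | 10% | 5% |

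Only perfect correlation brings the pair back to the level of a single test.

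**4. Two ways to control the pair.**
- *Fixed sequence, primary first.* If the primary null is true, any false claim needs a primary rejection, so the error is at most 10%. If only the exacerbation null is true, the error is that test's own 10%. The familywise error is therefore at most 10%, and the primary keeps 194 events and 79.9% power.
- *Equal split at 5% each.* Primary power falls to 70.0% at 194 events, or 247 events are needed for 80%.

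The sequence gives the control at no cost to the primary.

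**The case against.** The best defence is that Protocol 9.1 speaks of one hypothesis and is accurate about it. The 10% belongs to the primary test, and that test delivers it. The lack of adjustment is disclosed in SAP 3.3.5, and Protocol 9.4.2.2 foresaw the second logrank test, so the SAP did not slip it in. In a Phase IIa study with one powered hypothesis, unadjusted secondary analyses are ordinary. All of this stands. It leaves open why a secondary analysis carries the primary's rule for declaring efficacy with no statement of how the two relate. Disclosing that nothing is adjusted does not settle that.

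Several stronger readings are tempting, and the documents do not support them:
- *The trial fails to deliver its stated error rate.* No familywise or study-wide rate is stated, so none is missed.
- *The chance of a false benefit claim is well above 10%.* The 14–19% figures include results favouring placebo. In the beneficial direction the comparison is about 8–10% against 5%.
- *This is the key secondary endpoint.* The protocol uses that term only in general; neither document applies it to this endpoint.
- *The exacerbation p-value drives a go/no-go decision.* Protocol 9.5 and SAP 5 tie internal development decisions to the administrative interim analysis of the primary endpoint, which has no formal test.
- *The repeated-measures tests add further false claims.* SAP 3.4.3 does say "The study intervention effect will be tested at the 10% two-sided level of significance", but no evidence-of-efficacy rule is attached to those endpoints, and they are already reported with estimates and 90% confidence intervals. A label is enough for them.

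**Conclusion.** The point holds as a gap in the plan's logic. The single-test reason applies to the primary hypothesis only, and a second, unconditional efficacy rule stands beside it without error control. The primary conclusion, its 10% error, its power and its event count are unaffected. What is affected is the meaning of an exacerbation result when the primary fails.

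The sizes assume that both nulls are true and that the test statistics are jointly normal. Independence (19% two-sided, 9.75% in the beneficial direction) is the upper case in the range shown. The overlap of the endpoints makes a positive correlation more plausible, but its value is not known from the documents. This should be corrected; it does not threaten the trial's main result.

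**What to change.** In Protocol 9.1 and SAP 3.3.5 and 4.2.2.4, prespecify a fixed sequence. The exacerbation logrank test counts as evidence of efficacy only if the primary test has p ≤ 0.10 with a hazard ratio below 1. Otherwise, report its p-value as nominal beside the hazard ratio and 90% confidence interval. Naming the direction is useful in itself, because a two-sided p-value rule does not say which arm must do better. Add one sentence in SAP 3.3.5 that the p-values for all other secondary endpoints are nominal.

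If the sponsor does not want a hierarchy, the lighter alternative is to remove the efficacy rule from SAP 4.2.2.4 and call that p-value nominal throughout.

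The cost is a change of wording. The primary keeps its 194 events and roughly 80% power. The real price is that the exacerbation endpoint can no longer support an efficacy statement when the primary fails.

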9.2 Sample Size Determination

The study is powered using COPDCompEx, a composite endpoint used to predict treatment effect on moderate and severe exacerbations of COPD (see Section 8.2.1).

The time to first COPDCompEx event will be compared between mitiperstat (AZD4831) 5 mg QD vs placebo arms using a logrank test. A total of 194 first COPDCompEx events (estimated to require 203 participants per arm) will provide 80% power at the two-sided 10% level of statistical significance to detect a hazard ratio of 0.70 in the mitiperstat (AZD4831) 5 mg QD arm based on a 24-week first COPDCompEx event risk of 55% assumed in the placebo arm (constant over the course of the study).

A screen failure rate of 40% is assumed, therefore approximately 677 participants will be screened to achieve randomisation of 406 participants.

For all other secondary or exploratory endpoints, no formal sample size calculation was performed. Further information is available in the SAP.

9.3 Populations for Analyses

The following populations are defined:

 Table 7
 Populations for Analysis

Population/Analysis set	Description
Full Analysis Set (FAS)	Will include all randomised participants who received at least 1 dose of study intervention. Participants will be analysed according to planned treatment. Efficacy analyses will be based on the FAS.
Safety Analysis Set (SAF)	Will include all participants who received at least 1 dose of study intervention. Participants will be analysed according to actual treatment. Safety analyses will be based on the SAF.
Per Protocol Set (PP)	Will include all participants in the FAS who have no important protocol deviations thought to affect the analysis of COPDCompEx and FEV1 data.
PK Analysis Set	Will include all participants who received mitiperstat (AZD4831) and who have evaluable PK data for mitiperstat (AZD4831), with no important protocol deviations thought to impact on the analysis of the PK data.
Randomised Set	Will include all participants who have been randomised.
Cough subset	Will include the subset of FAS who consented to the cough substudy.

Participants will be analysed according to their randomised study intervention arm.

9.4 Statistical Analysis

9.4.1 General Considerations

The statistical methodology below describes the high-level statistical analysis as it is foreseen when the study is being planned.

All original and derived parameters as well as demographic and disposition data will be listed and described using summary statistics. Continuous data will be summarised using descriptive statistics (number of observations, mean, SD, median, 25th and 75th percentiles [where appropriate], minimum and maximum). In the case of log-transformed data, the geometric mean, CV% of geometric mean, median, minimum, and maximum will be presented. Frequencies and percentages will be used to summarise categorical data. Only the minimum, median, and maximum will be presented for time parameters such as t_{max} .

Deviations from the protocol will be assessed as "important" or "not-important" by **blinded** members of the study team.

Deviations will be defined before database hard lock and unblinding. Important deviations will include the following:

• Violation of inclusion and/or exclusion criteria

- Participants who developed withdrawal criteria during the study but were not withdrawn
- Wrong study intervention or incorrect dose administered
- Administration of prohibited concomitant medications that are expected to influence the measurement of the primary endpoint

A BDRM will be held before database hard lock and unblinding. The reasons for excluding participants or data from the study will be defined in the SAP and documented in the BDRM report.

9.4.2 Efficacy

9.4.2.1 Primary Endpoint

The primary endpoint to evaluate the clinical efficacy of mitiperstat (AZD4831) 5 mg compared with placebo is time to first COPDCompEx event. After at least 194 first COPDCompEx events have occurred, enrolment will be stopped and when the last participant completes 12 weeks of treatment, the study will stop (see Section 7.1.4). A logrank test and Cox's proportional hazards model will be used to analyse the time to first COPDCompEx event data. Survival probabilities will be presented as survival curves estimated using the Kaplan-Meier method. A two-sided logrank test P-value ≤ 0.10 is required to provide evidence of efficacy.

The primary estimand strategy for intercurrent events will be while on treatment and the supportive estimand strategy will be treatment policy (see Table 3). Model assumptions will be checked and mitigations for possible non-proportionality will be described in the SAP.

9.4.2.2 Secondary Endpoints

A similar approach to that described for the primary efficacy endpoint will be applied to the secondary endpoint: time to first exacerbation.

In order to ensure that the same event is not counted twice, concurrent moderate or severe COPD exacerbations with start and stop dates ≤ 7 days apart will be considered the same event and assigned the maximum severity between the two. Time during an exacerbation or in the 7 days following an exacerbation will not be included in the calculation of time at risk. However, the start day of a COPD exacerbation will not be excluded from the time at risk.

Any COPD exacerbation that occurs within 7 days of the last dose of systemic corticosteroids (oral, intramuscular, intravenous) or antibiotics or the last day of hospitalisation or emergency room visit for a prior COPD exacerbation will be combined and counted as a single exacerbation event and as the maximum severity between the individual events. Further details on combining exacerbation events will be provided in the SAP. Consistent criteria will be applied to all exacerbation endpoints.

Plasma concentrations will be summarised by timepoint in all participants. Pharmacokinetic data for those participants with additional PK sampling at Visit SV5 will be used to derive plasma PK parameters such as C_{max} and t_{max} .

9.4.2.3 Tertiary/Exploratory Endpoints

Details for the analyses of exploratory efficacy endpoints will be included in the SAP.

9.4.3 Safety

Adverse Events

Adverse events will be coded using the most recent version of MedDRA that will have been released for execution at AstraZeneca. Adverse events will be presented for each treatment group by system organ class and/or preferred term covering number and percentage of participants reporting at least one event and number of events where appropriate. An overview of AEs will be presented for each treatment group the number and percentage of participants with any AE, AEs with outcome of death, SAEs, and AEs leading to discontinuation of IP.

Separate AE tables will be provided taking into consideration seriousness, death, and events leading to discontinuation of IMP. An additional table will present number and percentage of participants with most common AEs. Most common (eg, frequency of > x%, $\ge x\%$) will be defined in the SAP. In accordance with the requirements of the FDA, a separate table will present non-serious AEs occurring in more than 5% of participants in any treatment group. Key participants information will be presented for participants with AEs with outcome of death, SAEs, and AEs leading to discontinuation of IMP. An AE listing for the SAF will cover details for each individual AE. AESIs related to skin reactions, including maculopapular rash, and infection, including pneumonia, will be presented. Full details of AE analyses will be provided in the SAP.

Vital Signs

Vital sign parameters will be presented for each treatment group. Summary statistics for continuous variables cover n, mean, SD, min, Q1, median, Q3, and max. For each scheduled post-baseline visit, descriptive statistics for all vital sign parameters will be presented for observed values and change from baseline. Details of vital sign analyses will be provided in the SAP.

Laboratory Parameters

Laboratory parameters will be presented for each treatment group. Summary statistics for continuous variables cover n, mean, SD, minimum, Q1, median, Q3, and maximum. For each scheduled post-baseline visit, descriptive statistics for all clinical chemistry and haematology parameters will be presented for observed values and change from baseline. A frequency table

presents the number of participants reporting at least one abnormality in selected laboratory parameters. Details of laboratory analyses will be provided in the SAP.

Electrocardiogram

Electrocardiogram parameters will be presented for each treatment group. Summary statistics for continuous variables cover n, mean, SD, minimum, Q1, median, Q3, and maximum. For each scheduled post-baseline assessment, descriptive statistics for all ECG parameters will be presented for observed values and change from baseline. Supportive ECG listings will cover observed values for each individual participant. Details of ECG analyses will be provided in the SAP.

9.5 Interim Analysis

An administrative IA will be conducted after 136 (70% of the required 194) first COPDCompEx events have occurred. It will allow an early assessment of efficacy for mitiperstat (AZD4831), according to the decision framework (Frewer et al 2016). No formal statistical test will be conducted. The IA assessment will be used to guide internal (AstraZeneca) decision-making regarding further development of the mitiperstat (AZD4831) programme. As a result, no alpha will be spent at the IA. A URC will be set up to review data from this administrative IA on the primary efficacy endpoint. (see Appendix A 5 for further details).

The URC charter will describe the planned administrative IA in greater detail.

9.6 Data Review Committee

The DRC members will be notified on an ongoing basis of all skin reaction and pneumonia events and can call a meeting at any time to discuss the event frequency. Although not part of the IA, the DRC will conduct an evaluation of safety at the time of the administrative IA, to allow efficacy IA outcome data to be considered should it be required. For details on the DRC for this study, see Appendix A 5.

10 SUPPORTING DOCUMENTATION AND OPERATIONAL CONSIDERATIONS

Appendix A Regulatory, Ethical, and Study Oversight Considerations

A 1 Regulatory and Ethical Considerations

- This study will be conducted in accordance with the protocol and with the following:
 - Consensus ethical principles derived from international guidelines including the
 Declaration of Helsinki as amended at 64th WMA General Assembly, Fortaleza,
 Brazil, October 2013 and Council for International Organizations of Medical Sciences
 (CIOMS) International Ethical Guidelines
 - Applicable ICH GCP Guidelines
 - Applicable laws and regulations
- The protocol, revised protocol, ICF, Investigator's Brochure, and other relevant documents (eg, advertisements) must be submitted to an IRB/IEC by the investigator and reviewed and approved by the IRB/IEC before the study is initiated.
- Any revised protocol will require IRB/IEC and applicable Regulatory Authority approval before implementation of changes made to the study design, except for changes necessary to eliminate an immediate hazard to study participants.
- AstraZeneca will be responsible for obtaining the required authorisations to conduct the study from the concerned Regulatory Authority. This responsibility may be delegated to a CRO but the accountability remains with AstraZeneca.
- The investigator will be responsible for providing oversight of the conduct of the study at the site and adherence to requirements of 21 CFR, ICH guidelines, the IRB/IEC, European Regulation 536/2014 for clinical studies (if applicable), European Medical Device Regulation 2017/745 for clinical device research (if applicable), and all other applicable local regulations

Regulatory Reporting Requirements for SAEs

- Prompt notification by the investigator to AstraZeneca of an SAE is essential so that legal obligations and ethical responsibilities towards the safety of participants and the safety of a study intervention under clinical investigation are met.
- AstraZeneca has a legal responsibility to notify both the local regulatory authority and other regulatory agencies about the safety of a study intervention under clinical investigation. AstraZeneca will comply with country-specific regulatory requirements relating to safety reporting to the regulatory authority, IRB/IEC, and investigators.
- Investigator safety reports must be prepared for suspected unexpected serious adverse reactions (SUSAR) according to local regulatory requirements and AstraZeneca policy and forwarded to investigators as necessary.
- Adherence to European Medical Device Regulation 2017/745 for clinical device research (if applicable), and all other applicable local regulations

 An investigator who receives an investigator safety report describing an SAE or other specific safety information (eg, summary or listing of SAEs) from AstraZeneca will review and then file it along with the Investigator's Brochure and other relevant documents and will notify the IRB/IEC, if appropriate according to local requirements.

Regulatory Reporting Requirements for Serious Breaches

- Prompt notification by the investigator to AstraZeneca of any (potential) serious breach of the protocol or regulations is essential so that legal and ethical obligations are met.
 - A 'serious breach' means a breach likely to affect to a significant degree the safety and rights of a participant or the reliability and robustness of the data generated in the clinical study.
- If any (potential) serious breach occurs in the course of the study, investigators or other site personnel will inform the appropriate AstraZeneca representatives immediately after he or she becomes aware of it.
- In certain regions/countries, AstraZeneca has a legal responsibility to notify both the local regulatory authority and other regulatory agencies about such breaches.
 - AstraZeneca will comply with country-specific regulatory requirements relating to serious breach reporting to the regulatory authority, IRB/IEC, and investigators. If EU Clinical Trials Regulation 536/2014 applies, AstraZeneca is required to enter details of serious breaches into the European Medicines Agency (EMA) Clinical Trial Information System (CTIS). It is important to note that redacted versions of serious breach reports will be available to the public via CTIS.
- The investigator should have a process in place to ensure that:
 - The site staff or service providers delegated by the investigator/institution are able to identify the occurrence of a (potential) serious breach
 - A (potential) serious breach is promptly reported to AstraZeneca or delegated party, through the contacts (email address or telephone number) provided by AstraZeneca.

A 2 Financial Disclosure

Investigators and sub-investigators will provide AstraZeneca with sufficient, accurate financial information as requested to allow AstraZeneca to submit complete and accurate financial certification or disclosure statements to the appropriate regulatory authorities. Investigators are responsible for providing information on financial interests during the study and for 1 year after completion of the study.

A 3 Informed Consent Process

- The investigator or his/her representative will explain the nature of the study to the participant or his/her legally authorised representative and answer all questions regarding the study.
- Participants must be informed that their participation is voluntary and they are free to
 refuse to participate and may withdraw their consent at any time and for any reason
 during the study. Participants or their legally authorised representative will be required to
 sign a statement of informed consent that meets the requirements of 21 CFR 50, local
 regulations, ICH guidelines, privacy and data protection requirements, where applicable,
 and the IRB/IEC or study centre.
- The medical record must include a statement that written informed consent was obtained before the participant was enrolled in the study and the date the written consent was obtained. The authorised person obtaining the informed consent must also sign the ICF.
- If new information requires changes to the ICF, consider if participants must be reconsented and if so, this must be to the most current version of the ICF(s) during their participation in the study.
- A copy of the ICF(s) must be provided to the participant or the participant's legally authorised representative.

Participants who are rescreened are required to sign a new ICF.

The ICF will contain a separate section that addresses and documents the collection and use of any mandatory and/or optional human biological samples. The investigator or authorised designee will explain to each participant the objectives of the analysis to be done on the samples and any potential future use. Participants will be told that they are free to refuse to participate in any optional samples or the future use and may withdraw their consent at any time and for any reason during the retention period.

A 4 Data Protection

- Participants will be assigned a unique identifier by AstraZeneca. Any participant records
 or datasets that are transferred to AstraZeneca will contain the identifier only; participant
 names or any information which would make the participant identifiable will not be
 transferred.
- The participant must be informed that his/her personal study-related data will be used by AstraZeneca in accordance with local data protection law. The level of disclosure and use of their data must also be explained to the participant in the informed consent
- The participant must be informed that his/her medical records may be examined by Clinical Quality Assurance auditors or other authorised personnel appointed by

AstraZeneca, by appropriate IRB/IEC members, and by inspectors from regulatory authorities.

- The participant must be informed that data will be collected only for the business needs. We will only collect and use the minimum amount of personal data to support our business activities and will not make personal data available to anyone (including internal staff) who is not authorised or does not have a business need to know the information.
- The participant must be informed that in some cases their data may be pseudonymised. The General Data Protection Regulation (GDPR) defines pseudonymisation as the processing of personal data in such a way that the personal data can no longer be attributed to a specific individual without the use of additional information, provided that such additional information is kept separately and protected by technical and organisational measures to ensure that the personal data are not attributed to an identified or identifiable natural person.

A 5 Committees Structure

- A URC consisting only of AstraZeneca personnel will require unblinding and will be independent from the study team. The URC will ensure that the IA is performed in a way that maintains the integrity of the study and in accordance with the IA unblinding plan. The URC will communicate to the study team as specified in the URC charter.
- A DRC consisting of AstraZeneca personnel, an external dermatologist, and an external pulmonologist will be set up for periodic safety monitoring, with a focus on skin reactions and pneumonia. The AstraZeneca personnel in the DRC will be independent from the study team. At the time of the IA, the DRC will assess the safety profile (ie, all AE data) of mitiperstat (AZD4831) and will have access to IA outcome data, if required. Additional details will be contained in the DRC Charter.

A 6 Dissemination of Clinical Study Data

A description of this clinical study will be available on http://astrazenecagrouptrials.pharmacm.com and http://www.clinicaltrials.gov as will the summary of the main study results when they are available. The clinical study and/or summary of main study results may also be available on other websites according to the regulations of the countries in which the CRESCENDO study is conducted.

A 7 Data Quality Assurance

• All participant data relating to the study will be recorded on eCRF unless transmitted to AstraZeneca or designee electronically (eg, laboratory data). The investigator is

- responsible for verifying that data entries are accurate and correct by electronically signing the eCRF.
- The investigator must maintain accurate documentation (source data) that supports the information entered in the eCRF.
- The investigator must permit study-related monitoring, audits, IRB/IEC review, and regulatory agency inspections and provide direct access to source data documents.
- Monitoring details describing strategy, including definition of study-critical data items
 and processes (eg, risk-based initiatives in operations and quality such as Risk
 Management and Mitigation Strategies and Analytical Risk-Based Monitoring), methods,
 responsibilities and requirements, including handling of noncompliance issues and
 monitoring techniques (central, remote, or on-site monitoring) are included in the
 Monitoring Plan.
- AstraZeneca or designee is responsible for medical oversight throughout the conduct of
 the study which includes clinical reviews of study data in accordance with the currently
 approved protocol. Monitoring details describing clinical reviews of study data from a
 medical perspective are included in more detail in the Monitoring Plan(s).
- AstraZeneca or designee is responsible for the data management of this study including quality checking of the data.
- AstraZeneca assumes accountability for actions delegated to other individuals (eg, CROs).
- Study monitors will perform ongoing source data verification as per the Monitoring Plan(s) to confirm that data entered into the eCRF by authorised site personnel are accurate, complete, and verifiable from source documents; that the safety and rights of participants are being protected; and that the study is being conducted in accordance with the currently approved protocol and any other study agreements, ICH GCP, and all applicable regulatory requirements.
- Records and documents, including signed ICFs, pertaining to the conduct of this study
 must be retained by the investigator for 25 years after study archiving or as required by
 local regulations, according to the AstraZeneca Global Retention and Disposal (GRAD)
 Schedule. No records may be destroyed during the retention period without the written
 approval of AstraZeneca. No records may be transferred to another location or party
 without written notification to AstraZeneca.

A 8 Source Documents

• Source documents provide evidence for the existence of the participant and substantiate the integrity of the data collected. Source documents are filed at the investigator's site.

- Data entered in the eCRF that are transcribed from source documents must be consistent with the source documents or the discrepancies must be explained. The investigator may need to request previous medical records or transfer records, depending on the study. Also, current medical records must be available.
- Definition of what constitutes source data can be found in the source data verification plan.

A 9 Study and Site Start and Closure

The study start date is the date on which the clinical study will be open for recruitment of participants.

The first act of recruitment is the first site open and will be the study start date.

AstraZeneca designee reserves the right to close the study site or terminate the study at any time for any reason at the sole discretion of AstraZeneca. Study sites will be closed upon study completion. A study site is considered closed when all required documents and study supplies have been collected and a study-site closure visit has been performed.

The investigator may initiate study-site closure at any time, provided there is reasonable cause and sufficient notice is given in advance of the intended termination.

Reasons for the early closure of a study site by AstraZeneca or investigator may include but are not limited to:

- Failure of the investigator to comply with the protocol, the requirements of the IRB/IEC or local health authorities, AstraZeneca's procedures, or GCP guidelines.
- Inadequate recruitment of participants by the investigator.
- Discontinuation of further study intervention development.

Reasons for the early termination of the study by AstraZeneca may include but are not limited to:

- The incidence, frequency, duration or severity of AEs in this or other studies exposing participants to undue harm.
- Participant enrolment is unsatisfactory.
- Non-compliance that might significantly jeopardise the validity or integrity of the study.
- AstraZeneca decision to terminate development of the investigational product for this indication.
- Unjustifiable risk resultant from the risk-benefit assessment conducted at the IA.

If the study is prematurely terminated or suspended, AstraZeneca shall promptly inform the investigators, the IECs/IRBs, the regulatory authorities, and any CRO(s) used in the study of the reason for termination or suspension, as specified by the applicable regulatory requirements. The investigator shall promptly inform the participant and should assure appropriate participant therapy and/or follow-up.

Participants from terminated sites will have the opportunity to be transferred to another site to continue the study.

A 10 Publication Policy

- The results of this study may be published or presented at scientific meetings. If this is foreseen, the investigator agrees to submit all manuscripts or abstracts to AstraZeneca before submission. This allows AstraZeneca to protect proprietary information and to provide comments.
- AstraZeneca will comply with the requirements for publication of study results. In accordance with standard editorial and ethical practice, AstraZeneca will generally support publication of multicentre studies only in their entirety and not as individual site data. In this case, a coordinating investigator will be designated by mutual agreement.
- Authorship will be determined by mutual agreement and in line with International Committee of Medical Journal Editors authorship requirements.

Appendix B Adverse Events: Definitions and Procedures for Recording, Evaluating, Follow-up, and Reporting

B 1 Definition of Adverse Events

An AE is the development of any untoward medical occurrence in a patient or clinical study participant administered a medicinal product and which does not necessarily have a causal relationship with this treatment. An AE can therefore be any unfavourable and unintended sign (eg, an abnormal laboratory finding), symptom (for example nausea, chest pain), or disease temporally associated with the use of a medicinal product, whether considered related to the medicinal product.

